9.1.1. Primary Design - Comparative Cohort Design

A comparative cohort design will be used to estimate incidence rates and incidence rate ratios of prespecified outcomes among immunocompromised, or renally impaired, or hepatically impaired older adults with and without receipt of the ABRYSVO vaccine. Individuals in the unvaccinated cohort must have no record of an RSV vaccine on the index date or in the baseline period prior to index date or any other vaccine on the index date but can later receive ABRYSVO and enter the vaccinated cohort if all eligibility criteria are met. To address possible selection bias due to health seeking behaviours, unvaccinated individuals will be randomly selected from a population of patients who have regular use of preventive medical care, defined as at least one vaccination record in the year prior to the index date. The baseline period is defined as 12 months prior to the index date. The follow-up period will begin from day 1 (the day after ABRYSVO administration for vaccinated cohort, or the day after matched index date for the unvaccinated cohort) and continue to the earliest occurrence of an outcome, date of RSV vaccination (for unvaccinated individuals who later receive any RSV vaccine only), the end of administrative follow-up, end of the study period, or death. For those outcomes with a defined risk window, follow-up will also be truncated at the end of the risk window. To enhance comparability between the vaccinated and unvaccinated cohorts, ATT weights will be used. Weights, based on PS, will incorporate additional measures of healthcare utilization in the baseline period to further account for potential differences in healthcare seeking behaviour between the vaccinated and unvaccinated cohorts. However, as this study focuses on patients with chronically managed conditions, differences in healthcare seeking behaviour are not anticipated. IPCW will also be employed if informative censoring (i.e., differential rates of censoring during follow up) and high censoring rates are observed between the vaccinated and unvaccinated cohorts. Examples of patient follow-up scenarios are depicted in Figure 1 and Figure 2. Comparative analyses will also include variables that remain inadequately balanced between the two cohorts in a doubly robust approach. Further details are provided in Section 9.7.2 and Section 9.7.3.

Figure 1 Comparative Cohort Design

[figure not shown]

Notes:

a. Baseline conditions include comorbidities of interest, medications of interest, vaccination, healthcare utilisation, and/or surrogates of frailty.

b. Earliest of outcome of interest, receipt of RSV vaccine (for unvaccinated cohort), death, end of administrative enrollment, end of the study period (or risk window if applicable).

Figure 2 Index Matching and Follow-up Scenarios for Vaccinated and Unvaccinated in Comparative Cohort Design

O is occurrence of outcome of interest; V is vaccination with ABRYSVO, X is censoring event prior to end of study period

Notes:

Three scenarios: (a) Persons 1 and 2: during follow up the vaccinated individual has an outcome of interest; the unvaccinated control is censored at the date of vaccination of the control (b) Persons 3 and 4: follow up for the vaccinated person continues until follow up is censored at the end of the risk window while the control is followed until an outcome is observed, and; (c) Person 5 and 6: a control (Person 6) is index-matched for Person 5 at the time of vaccination and the pair are followed until the end of the study period. Neither experience an outcome of interest.

PFIZER CONFIDENTIAL CT24-WI-GL02-RF02 5.0 Non-Interventional Study Protocol Template For Secondary Data Collection Study 01-Aug-2023 Page 22 of 72

9.1.2. Self-controlled Risk Interval (SCRI) Design

[figure not shown]
A SCRI design will be used for a subset of study outcomes that meet the necessary study design assumptions, as a complementary analytic approach. The assumptions for a SCRI design include that the outcome must have acute onset and short latency, as well as a relatively well-defined risk interval. The assumptions underpinning the SCRI also require that occurrence of the outcome does not affect the probability of exposure. Table 1 in Section 9.3 indicates outcomes for which a SCRI analysis is deemed a valid approach.

The SCRI design uses information from cases (i.e, vaccinated individuals who experience an outcome) to compare the incidence of an outcome in the risk interval following vaccination to the incidence in a post-vaccination control interval within the same individual.^{22, 23}

Unlike the comparative cohort design, which may suffer from potential vaccine exposure under-ascertainment and misclassification as well as potential residual confounding, the SCRI design is a within person analysis that implicitly controls for time invariant confounders. Time varying confounders still need to be controlled for but with short, defined risk windows, the risk of time varying confounding is limited.

Risk intervals will be applied starting on the day after vaccination (Day 1), for a duration of time specific to each outcome; Table 1 in Section 9.3 defines the risk interval proposed for each outcome. A prespecified post-vaccination control interval will be used for each outcome of interest. The post-vaccination control interval will occur after the risk interval associated with ABRYSVO administration to avoid potential differential reporting of outcome in the pre- and post-vaccination periods. The risk and control intervals are based on a review of the published literature and precedence from previous studies of vaccine safety (see Table 1). As an example, the SCRI design with 42-day risk interval and 42-day post-vaccination control interval for Guillain-Barré syndrome (GBS) is presented in Figure 3 below.

Figure 3 Self-controlled Risk Interval Design

PFIZER CONFIDENTIAL CT24-WI-GL02-RF02 5.0 Non-Interventional Study Protocol Template For Secondary Data Collection Study 01-Aug-2023 Page 23 of 72

9.2. Setting

For the implementation of this study, we will use electronic healthcare databases in Europe. The selected data sources and two-letter country codes are as follows:

- Clinical Practice Research Datalink (CPRD) Aurum (UK)
- Valencia Health System Integrated Database (VID) (ES)
- Information System for the Improvement of Research in Primary Care (Sistema d'Informació per al Desenvolupament de la Investigació en Atenció Primària [SIDIAP]) (ES)
- EpiChron Research Group on Chronic Diseases at the Aragon Health Sciences Institute (EpiChron) (ES)
- Système National des Données de Santé (SNDS) (FR)

9.2.1. Inclusion Criteria

Patients meeting the following criteria will be included in the study:

- Vaccinated Cohort: Vaccination with ABRYSVO
- *Unvaccinated Cohort:* No vaccination with ABRYSVO or other vaccines on the index date
- *Unvaccinated Cohort:* No vaccination with any RSV vaccine in the 12-months prior to index
- Each population of immunocompromised or renally impaired or hepatically impaired individuals must meet the population-specific inclusion criteria in Section 9.2.1.1, Section 9.2.1.2, and Section 9.2.1.3, respectively
- Age 60 years and older at index date
- A minimum of 12 months of administrative enrollment history prior to index in one of the selected data sources to ensure adequate characterisation of medical history
- A minimum of one day of follow up post-index
- For analyses of outcomes assessed with the SCRI design, the following additional criteria must be met. Note that the study population for each outcome-specific analysis will thus be different
 - a. Have received ABRYSVO
 - b. Have experienced an event of interest during the risk or control interval
 - c. Have full accrual of data used to define the event in the risk and control intervals combined, after accounting for any data lag and timing of data extraction

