9.3.1.1. Comparative Cohort Design

The exposure cohorts for the comparative cohort design will be defined as follows:

• The vaccinated cohort will be defined as individuals who were administered ABRYSVO.

To be included in the unvaccinated cohort, individuals must meet the following criteria:

• No vaccine record on index date: They must not have a record of receiving any vaccine, including the RSV vaccines, on the index date.

PFIZER CONFIDENTIAL

CT24-WI-GL02-RF02 5.0 Non-Interventional Study Protocol Template For Secondary Data Collection Study 01-Aug-2023 Page 29 of 72 • **No RSV vaccination in baseline period**: They must not have a record of receiving any RSV vaccine during the 12-month baseline before the index date.

Note: If individuals in the unvaccinated cohort receive ABRYSVO during the follow-up period, they will be censored in the unvaccinated cohort and become eligible for inclusion in the vaccinated cohort if all other eligibility criteria are met.

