9.7.3.1. Comparison with Unvaccinated Cohort

For each of the immunocompromised, renally impaired or hepatically impaired populations respectively, the incidence rates of the prespecified outcomes following administration of ABRYSVO will be compared against the incidence rates of the prespecified outcomes among individuals who did not receive ABRYSVO or any other vaccine at index.

An ATT weighting will be used to ensure baseline comparability between the ABRYSVO vaccinated cohort and unvaccinated cohort. ATT weighting creates a "pseudo-population" in which the distribution of covariates is, on average, the same in each cohort.⁵⁷ Specifically, ATT weights will be calculated to allow for estimation of the average treatment effect among individuals receiving ABRYSVO.⁵⁷ This approach will be taken to ensure that inference from the analysis will be applicable to the vaccinated population. Individuals receiving ABRYSVO will receive an ATT weight of one. Individuals not receiving ABRYSVO will receive an ATT weight equal to the odds of receiving ABRYSVO conditional on their demographic and clinical characteristics as of the index date, which will be calculated based

PFIZER CONFIDENTIAL CT24-WI-GL02-RF02 5.0 Non-Interventional Study Protocol Template For Secondary Data Collection Study 01-Aug-2023 Page 46 of 72 on the PS. The PS is defined as an individual's probability of receiving ABRYSVO, conditional on observed baseline covariates, and will be calculated using a logistic regression model. To select the variables to be included in the PS logistic model, a systematic approach based on clinical relevance, prior research, and statistical criteria will be used. The PS logistic regression model may include the cohort variable (i.e, ABRYSVO versus unvaccinated control) as the dependent variable, the independent variables that are deemed clinically important and have shown good control of confounding for previous comparative vaccine studies (e.g., age, sex, place of residence, co-morbidity indices, socioeconomic status/education level),⁵⁸ and baseline covariates that have crude standardized differences $\geq 10\%$ between the two cohorts. Specifically, ATT weights will be PS/(1-PS) for individuals with no record of ABRYSVO. The distribution of weights will be examined to assess extreme values, and truncation will be considered if necessary.

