- Descriptive analyses will be conducted to assess whether there is differential receipt of other vaccines in the follow up period between the vaccinated and unvaccinated cohort (comparative cohort design) and between the risk and control intervals (SCRI design). Differential receipt of vaccines during follow up may introduce potential time varying confounding. If differential patterns of vaccination during follow up are observed, the following approaches may be considered:
 - Comparative cohort analysis with censoring at receipt of another vaccine during follow-up
 - SCRI with analyses stratified by those who did and did not receive vaccinations during the risk or control interval
 - For individuals with receipt of other vaccines close to index (e.g.,30 or 45 days prior to index), comparative cohort and SCRI analyses will be repeated excluding those individuals
- Quantitative bias analysis to assess potential unmeasured confounding (comparative cohort)
- Negative control outcome analyses will be considered to assess potential unmeasured confounding, selection bias, and misclassification bias (for both comparative cohort and SCRI designs). As different AESIs may be associated with different care and medical encounter patterns reflecting different bias structures, careful consideration should be given to which negative controls are appropriate for which AESI analyses. As such, several negative controls may be considered for inclusion, including, but not limited to, accidental poisoning, appendicitis, cataracts, or non-vertebral fractures. Further details on the choice of negative control outcomes will be described in the SAP.

Further details and any additional sensitivity analyses that may be conducted will be described in the SAP.

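### Comparators may not have any vaccine on the index date but ABRYSVO recipients may, and no committed analysis separates a same-day vaccine's effect from ABRYSVO's in the short-window outcomes

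*Protocol*

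**What the plan says.** **Same-day rule.** Section 9.2.1 requires of the unvaccinated cohort "No vaccination with ABRYSVO or other vaccines on the index date". Section 9.3.1.1 repeats it: "They must not have a record of receiving any vaccine, including the RSV vaccines, on the index date". Section 9.1.1 has the same bar, and section 9.7.3.1 describes the comparison group as "individuals who did not receive ABRYSVO or any other vaccine at index". For the exposed side, section 9.3.1.1 says only "The vaccinated cohort will be defined as individuals who were administered ABRYSVO". Neither the inclusion criteria nor the exclusions in section 9.2.2 limit other vaccines that recipients get on the same day. Section 9.7.3.1 adds "Individuals receiving ABRYSVO will receive an ATT weight of one", so every recipient stays in the target population.

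**Other-vaccine analyses.** Section 9.7.4 first describes vaccines received during follow-up. If the patterns differ, it lists options that may be considered: censoring at another vaccine in the cohort design, stratifying the SCRI, and a third that begins "For individuals with receipt of other vaccines close to index (e.g.,30 or 45 days prior to index". Section 9.9 covers the same two periods, shortly before index and during follow-up.

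**Prior-year rule.** Section 9.1.1 states that "unvaccinated individuals will be randomly selected from a population of patients who have regular use of preventive medical care", which is "defined as at least one vaccination record in the year prior to the index date". The rule is set for comparators only and does not appear in sections 9.2.1 or 9.3.1.1.

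**The concern.** The research question is about ABRYSVO. If some recipients get another vaccine at the same visit and comparators by rule do not, any acute reaction to that vaccine is counted on the ABRYSVO side. This matters most for outcomes with windows of days to weeks in Table 1, such as anaphylaxis, Guillain-Barré syndrome (GBS), Bell's palsy, convulsion and myocarditis. There an acute effect of a second vaccine would fall inside the window. A raised IRR could not then be assigned to ABRYSVO alone.

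The prior-year rule raises a smaller question. It is meant to make the cohorts alike in health-seeking, but only one cohort has to meet it.

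**Working it through.** **1. Can the planned methods adjust for a same-day vaccine?**

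- *Weighting.* Comparators are weighted by PS/(1-PS) and recipients by 1. A same-day vaccine has probability zero among comparators, so no weight can give coadministered recipients a counterpart.
- *Doubly robust step (9.7.3.1).* An indicator for a same-day vaccine is constant among comparators. Its coefficient would come from recipients alone, so no comparator informs the contrast for coadministered recipients.
- *SCRI.* Both vaccines are given on Day 0, so the risk interval follows both. The design removes fixed characteristics of the person, not a second exposure given at the same time.
- *Section 9.7.4.* Section 9.1.1 starts follow-up on Day 1, so the follow-up checks do not ordinarily see Day 0. The near-index exclusion gives days before index as its example and sits under the same condition. The exception is an SCRI window that starts on Day 0 (anaphylaxis 0-1, generalised convulsion 0-42). There, stratifying by vaccines received in the risk interval could reach same-day receipt, but it is optional.

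**2. How large could the effect be?**

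The protocol gives none of the inputs, so all three are assumed:
- q: share of recipients with another vaccine on Day 0
- p: share of comparators whose window includes the effect of another vaccine
- RRc: rate ratio of that vaccine within the window

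With a true ABRYSVO IRR of 1, equal background rates and no interaction:

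IRR ≈ [1 + q(RRc-1)] / [1 + p(RRc-1)]

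| q | RRc | p = 0 | p = 0.2 |
|---|---|---|---|
| 0.2 | 1.5 | 1.10 | 1.10/1.10 = 1.00 |
| 0.3 | 2 | 1.30 | 1.30/1.20 = 1.08 |
| 0.5 | 2 | 1.50 | 1.50/1.20 = 1.25 |
| 0.5 | 3 | 2.00 | 2.00/1.40 = 1.43 |

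For RRc above 1, the ratio falls below 1 when p exceeds q.

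**3. Is that visible at the planned scale?**

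Table 2 for GBS uses a risk of L0 = 0.0000069 per person, IRR 2, two-sided alpha 0.05, 80% power and 1:1 cohorts.

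n = (1.960 + 0.842)² × (L0 + L1)/(L1 - L0)² = 7.849 × 3/0.0000069 = 3,412,557 per cohort, as the protocol states.

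At that size, let a = 1 + q(RRc-1) and b = 1 + p(RRc-1). The standardised difference is t = (a - b) × √(n·L0/(a + b)), with n·L0 = 23.55. The chance of a two-sided 5% signal when ABRYSVO has no effect is Φ(t - 1.96) + Φ(-t - 1.96):

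| q | RRc | p = 0 | p = 0.2 |
|---|---|---|---|
| 0.3 | 2 | 16% | 6% |
| 0.5 | 2 | 34% | 14% |
| 0.5 | 3 | 80% | 35% |

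For example, at q = 0.5, RRc = 3, p = 0.2: t = 0.6 × √(23.55/3.4) = 1.58, giving 35%.

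**4. Prior-year rule.**

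Suppose a share u of recipients has no prior-year vaccination and a background rate r times that of the others, with all else balanced. The null IRR is (1 - u) + u·r. At u = 0.2 and r from 0.5 to 1.5 (assumed) it runs from 0.90 to 1.10, so the direction is not known.

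**The case against.** **The comparators are not a never-vaccinated group.** A reader might infer that the contrast is against no vaccine at all. The text does not support that. The bar covers one day. Every comparator has a vaccination in the prior year, possibly just before index. Comparators are matched on calendar time, and follow-up is censored only for RSV vaccines, so they can receive influenza or COVID-19 vaccine from Day 1. This stands. It makes 1 + q(RRc-1) an upper bound, which is why p is in the formula.

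**The sensitivity analyses are not blind to Day 0 by construction.** The 30 or 45 days are an example, so the near-index exclusion could be read to include Day 0. The SCRI stratification reaches Day 0 for two outcomes, section 9.9 says more firmly that imbalance will lead to additional analyses, and other vaccinations are covariates assessed at or before index. This stands in part: it rules out saying that same-day receipt can never be examined. But no same-day analysis is committed, and section 9.9 also speaks only of vaccines before index and during follow-up.

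**It may belong in the statistical analysis plan.** Further sensitivity analyses are deferred there, and one may cover this. But the one-sided eligibility rule is fixed in the protocol, so the protocol should also carry the analysis that offsets it.

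**The prior-year rule is a defensible proxy.** Recipients have shown vaccine uptake by being vaccinated; comparators must show it another way. A reader might infer that the effect in recipients without a prior-year vaccine is not identified. That holds only if prior-year vaccination is needed for comparability beyond the utilisation and preventive-care covariates, which the document does not establish. Imposing the rule on recipients in the primary analysis would also change the vaccinated population that the weights are meant to represent.

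**Conclusion.** The same-day asymmetry is real and is written into eligibility. Neither design can separate a coadministered vaccine's acute effect from ABRYSVO's, and the protocol commits to no analysis that does. A raised IRR in a short-window outcome could therefore be partly due to another vaccine.

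The size cannot be stated from the document. Over the assumed values tabulated, the null IRR runs from 1.10 to 2.00 if no comparator is vaccinated in the window, and from 1.00 to 1.43 if 20% are. The figure of 2.00 combines the highest assumed values of q and RRc with p = 0 and should not be read as expected. The point does not carry over with the same force to the 365-day outcomes, where a short-lived effect is diluted.

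The prior-year rule is a lesser matter: a drafting gap in the formal criteria and a one-sided restriction whose effect could go either way. It does not call for a change to the primary cohort.

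**What to change.** 1. In section 9.7.4, prespecify, without any trigger, an analysis of the short-window outcomes in both designs that excludes recipients with another vaccine on Day 0. Report coadministered recipients as a separate stratum where numbers allow.
2. Reword the near-index exclusion so that its window includes Day 0.
3. List the prior-year vaccination rule for comparators in sections 9.2.1 and 9.3.1.1. Add a sensitivity analysis restricting recipients to those with a vaccination record in the year strictly before index, and leave the primary cohort as it is.

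The cost is protocol and analysis-plan wording and further runs of existing code. The restricted analyses will have fewer vaccinated persons and wider intervals. Comparative results are due only in the final report (28 September 2029), so the change can precede them.

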8.2. Objectives

Primary Study Objective

To estimate the incidence rates and rate ratios of safety events of interest in immunocompromised or renally or hepatically impaired adults aged 60 years and older who receive ABRYSVO compared to a relevant comparator group who does not receive ABRYSVO (evaluated as separate populations and if appropriate, as a combined population).

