9.2.2. Exclusion Criteria

Patients meeting any of the following criteria will not be included in the study:

- 1. Have a diagnosis for the specific outcome under study within the 12 months prior to the index date (to distinguish the recording of previous events from true new events) and at any time prior to the index date for diabetes type 1
- 2. Have received any RSV vaccinations during the 12-month baseline period

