9.2.4. Study Period

The study period will start from 23 August 2022 to allow at least 12 months of administrative enrolment before vaccination with vaccination possible from the date of approval in the EU. Data collection will extend through a minimum of three vaccination seasons (2023, 2024, and 2025). Patient follow-up will last for up to 12 months post-vaccination depending on the outcome; therefore, data collection will extend through the end of 2026, at a minimum. Vaccine uptake will be periodically monitored to inform the overall length of the study period, and additional vaccination seasons (with 12-month post-vaccination follow-up) may be added based on vaccine uptake and exposure accrual. Time lags for data availability will be taken into account for analysis and reporting purposes.

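### The RSV-vaccine exclusion looks back only 12 months in a study of at least three seasons, so people vaccinated in an earlier season can be sampled as unvaccinated comparators

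*Protocol*

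**What the plan says.** Protocol section 9.2.1 requires of the unvaccinated cohort "No vaccination with any RSV vaccine in the 12-months prior to index". Section 9.2.2 excludes from either cohort people who "Have received any RSV vaccinations during the 12-month baseline period". Section 9.3.1.1 repeats the limit for the unvaccinated cohort: "They must not have a record of receiving any RSV vaccine during the 12-month baseline before the index date". Section 9.1.1 says these people "must have no record of an RSV vaccine on the index date or in the baseline period prior to index date" and adds that "The baseline period is defined as 12 months prior to the index date". The abstract uses the same 12 months. No section says ever, or since launch.

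On timing, section 9.2.4 starts the study period on 23 August 2022 "to allow at least 12 months of administrative enrolment before vaccination with vaccination possible from the date of approval in the EU", and states "Data collection will extend through a minimum of three vaccination seasons (2023, 2024, and 2025"; further seasons may be added.

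On the comparator, the objective in section 8.2 is a rate ratio "compared to a relevant comparator group who does not receive ABRYSVO", and section 9.1 describes a random sample of unvaccinated older adults.

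**The concern.** The look-back is shorter than the span of index dates. The protocol deals with movement in one direction: a comparator who later receives an RSV vaccine is censored and, if the vaccine was ABRYSVO, may join the vaccinated cohort. It is silent on the reverse, a vaccinee whose dose has aged past 12 months. Censoring comparators at RSV vaccination shows that the authors do not regard post-vaccination time as comparator time, yet the same person may return to the comparator pool a year later.

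Two features bear on this. Section 9.1.1 draws comparators from people with at least one vaccination record in the prior year. That favours people who accept vaccines and so plausibly favours earlier RSV vaccinees, though no share is given. The other-vaccinations list in section 9.3.3 omits RSV vaccine. Covariates there are assessed at index or in the 12-month baseline, so an RSV item measured in that window would be empty by construction. The propensity score as listed cannot adjust for an earlier dose.

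At stake are the meaning of the comparator and, if any effect outlasts 12 months, a bias towards no difference. In a safety study that is the direction that hides harm.

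**Working it through.** **1. Dates.** Inputs: first possible ABRYSVO vaccination on 23 August 2023 (section 9.2.4) and a 12-month look-back (section 9.2.1). Adding 366 days to the vaccination date:

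| Vaccinated | Meets the comparator RSV criterion from about |
|---|---|
| 23 Aug 2023 | 23 Aug 2024 |
| 15 Oct 2023 | 15 Oct 2024 |
| 31 Dec 2023 | 31 Dec 2024 |
| 15 Oct 2024 | 16 Oct 2025 |
| 31 Dec 2024 | 1 Jan 2026 |

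Index dates before late August 2024 carry no earlier ABRYSVO vaccinees. From then on, 2023 vaccinees can enter. From late 2025, those vaccinated in autumn 2024 can enter too. They must still meet every other criterion and be sampled.

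**2. The plan's own figure.** Table 2 gives 1,178 per cohort for arrhythmia at a rate ratio of 2, with background risk 0.02 over 365 days, 80% power and two-sided alpha 0.05. For a comparison of two Poisson rates,

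n = (1.960 + 0.842)² × (λ1 + λ0) / (λ1 − λ0)² = 7.849 × 0.06 / 0.02² = 1,177.3, rounded up to 1,178.

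This reproduces Table 2, as do its other 23 sample sizes. Table 2 is sound for a comparator with no earlier vaccinees.

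**3. Illustration of dilution.** Let f be the weighted share of comparators vaccinated in an earlier season, and c the share of the excess rate that persists beyond 12 months. Neither is in the protocol; both are assumed. With true ratio R,

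comparator rate = λ0 × [1 + f·c·(R − 1)], and observed ratio = R / [1 + f·c·(R − 1)].

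For R = 2, λ0 = 0.02, λ1 = 0.04 and 1,178 per cohort:

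| f | c | Comparator rate | Observed ratio | Power | n for 80% |
|---|---|---|---|---|---|
| any | 0 | 0.0200 | 2.00 | 80% | 1,178 |
| 5% | 0.5 | 0.0205 | 1.95 | 77.7% | 1,249 |
| 10% | 0.5 | 0.0210 | 1.90 | 75.2% | 1,327 |
| 20% | 1 | 0.0240 | 1.67 | 58.3% | 1,963 |

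Example for the last row: 2 / 1.2 = 1.67; the standard error is √(0.064 / 1,178) = 0.00737; 0.016 / 0.00737 − 1.96 = 0.21, and Φ(0.21) = 0.583.

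**4. Which outcomes.** Of the 26 rows in Table 1, nine have a 365-day window: type 1 diabetes, narcolepsy, arrhythmia, coronary artery disease, heart failure, microangiopathy, stress cardiomyopathy, acute respiratory distress syndrome and death. The other 17 have windows of 42 days or less. On the plan's own windows, a person more than a year past a dose is outside every one.

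**5. Whether anything else catches it.** Section 9.7.4 includes an analysis excluding people vaccinated shortly before index, but it concerns other vaccines within about 30 or 45 days. Section 9.9 discusses vaccinations missing from the records and other vaccines near index, not recorded RSV vaccination more than 12 months back.

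**The case against.** The strongest reply is that 12 months is a coherent washout. It equals the longest risk window in Table 1 and the maximum follow-up in section 9.2.4, so on the protocol's assumptions an earlier vaccinee has no remaining excess risk at re-entry. Section 9.7.3.1 also defines the comparison by what was received at index, and the objective could be read that way. For many acute outcomes the self-controlled analysis uses vaccinated cases only, so the make-up of the comparator cannot affect it.

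Much of this stands. With no persistence, direct dilution is nil. But the protocol does not present the 12 months as a washout or give a reason for it, and it calls the cohort unvaccinated throughout. The self-controlled design is not planned in Table 1 for any of the 365-day outcomes, where persistence would matter most.

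A reader might infer that a large part of the later comparator group is exposed and that rate ratios are materially diluted. The documents do not support that: they give no uptake figure, no propensity odds for earlier vaccinees and no evidence of effects beyond 12 months. The first season contributes no earlier ABRYSVO vaccinees, and calendar matching keeps many of the previous season's vaccinees inside the 12-month exclusion.

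A reader might also infer that people will enter the vaccinated cohort twice. The criteria would allow a repeat dose after 12 months to qualify, but the protocol describes a single dose and does not mention revaccination. A repeat dose would in any case be a real exposure.

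**Conclusion.** The point holds on the text. The criterion is fixed the same way in four sections and the abstract, the minimum span of index dates exceeds it, and it lets in people who contradict the stated comparator. No sensitivity analysis or limitation covers this.

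The size cannot be determined from the protocol. Without persistence beyond 12 months, two things remain. One is selection: re-entrants are those who came through at least a year after an earlier dose, with no clear direction of bias. The other is a cohort that is not what its label says. With persistence, true ratios above 1 are pulled towards 1, mainly for the nine 365-day outcomes. The values 1.90 and 1.67 illustrate that mechanism under assumed f and c; they are not estimates of likely bias. Table 2 needs no correction.

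**What to change.** In sections 9.1.1, 9.2.1, 9.2.2 and 9.3.1.1, and in the abstract, exclude from the unvaccinated cohort anyone with any recorded RSV vaccination before the index date (in practice, since RSV vaccines became available). Keep 12 months as the minimum enrolment. For symmetry, index the vaccinated cohort in the primary analysis at the first recorded RSV vaccine dose, and report any repeat-dose recipients separately.

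If the 12-month limit is a deliberate washout, the second-best course is to say so and justify it, rename the comparator, and add a sensitivity analysis that excludes everyone previously vaccinated.

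The work is small, because RSV vaccination records are already needed to define exposure and censoring. There is a cost, however. Some comparators are lost, repeat-dose recipients and their events leave the primary analysis, and, since only 12 months of history is guaranteed, the effective look-back will differ between people. The protocol should state that last limitation.
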